**Investigator Interests:**

Does the principal investigator, or do any research personnel who are responsible for the design, conduct or reporting of this project or any of their family members (spouse or dependent child) have an incentive or interest, financial or otherwise, that may affect the protection of the human subjects involved in this project, the scientific objectivity of the research or its integrity? Note: The Principal Investigator (Project Director), upon consideration of the individual's role and

degree of independence in carrying out the work, will determine who is responsible for the design, conduct, or reporting of the research.

See Disclosures and Management of Personal Interests in Human Research

<http://www.yale.edu/hrpp/policies/index.html#COI>

Yes       No

Do you or does anyone on the research team who is determined by you to be responsible for the design, conduct or reporting of this research have any patent (sole right to make, use or sell an invention) or copyright (exclusive rights to an original work) interests related to this research protocol?

Yes       No

If yes to either question above, list names of the investigator or responsible person:

*The Yale University Principal Investigator, all Yale University co-investigators, and all Yale University individuals who are responsible for the design, conduct or reporting of research must have a current financial disclosure form on file with the University's Conflict of Interest Office. Yale New Haven Hospital personnel who are listed as co-investigators on a protocol with a Yale University Principal Investigator must also have a current financial disclosure form on file with the University's Conflict of Interest Office. If this has not been done, the individual(s) should follow this link to the COI Office Website to complete the form: <http://www.yale.edu/coi/>*

NOTE: The requirement for maintaining a current disclosure form on file with the University's Conflict of Interest Office extends primarily to Yale University and Yale-New Haven Hospital personnel. **Whether or not they are required to maintain a disclosure form with the University's Conflict of Interest Office, all investigators and individuals deemed otherwise responsible by the PI who are listed on the protocol are required to disclose to the PI any interests that are specific to this protocol.**

## SECTION II: GENERAL INFORMATION

1. **Performing Organizations:** Identify the hospital, in-patient or outpatient facility, school or other agency that will serve as the location of the research. Choose all that apply:

**a. Internal Location[s] of the Study:**

- |  |   |
|--|---|
|  Magnetic Resonance Research Center (MR-TAC)     |  Yale University PET Center                   |
|  Yale Cancer Center/Clinical Trials Office (CTO) |  YCCI/Church Street Research Unit (CSRU)      |
|  Yale Cancer Center/Smilow                       |  YCCI/Hospital Research Unit (HRU)            |
|  Yale-New Haven Hospital              |  YCCI/Keck Laboratories                       |
|  Cancer Data Repository/Tumor Registry           |  Yale-New Haven Hospital—Saint Raphael Campus |
|  Specify Other Yale Location:                    |   |

**b. External Location[s]:**

- |   |  |
|---|--|
|  APT Foundation, Inc.                       |  Haskins Laboratories                                  |
|  Connecticut Mental Health Center           |  John B. Pierce Laboratory, Inc.                       |
|  Clinical Neuroscience Research Unit (CNRU) |  Veterans Affairs Hospital, West Haven                 |
|  Other Locations, Specify:                  |  International Research Site
(Specify location(s)): |

**c. Additional Required Documents (check all that apply):**

- |  |   |
|--|---|
|  *YCCI-Scientific and Safety Committee (YCCI-SSC)  |  N/A |
|  *Pediatric Protocol Review Committee (PPRC)   | Approval Date:                          |
|  *YCC Protocol Review Committee (YRC-PRC)  | Approval Date:                          |
|  *Dept. of Veterans Affairs, West Haven VA HSS   | Approval Date:                          |
|  *Radioactive Drug Research Committee (RDRC)   | Approval Date:                          |
|  YNHH-Radiation Safety Committee (YNHH-RSC)  | Approval Date:                          |
|  Yale University RSC (YU-RSC)  | Approval Date:                          |
|  Magnetic Resonance Research Center PRC (MRRC-PRC)   | Approval Date:                          |
|  *Nursing Research Committee   | Approval Date:                          |
|  YSM/YNHH Cancer Data Repository (CaDR)  | Approval Date:                          |
|  Dept. of Lab Medicine request for services or specimens form  |   |
|  Imaging on YNHH Diagnostic Radiology equipment request form (YDRCTO request) found at http://radiology.yale.edu/research/ClinTrials.aspx |   |

*\*Approval from these committees is required before final HIC approval is granted. See instructions for documents required for initial submission and approval of the protocol. Allow sufficient time for these requests. Check with the oversight body for their time requirements.*

2. **Probable Duration of Project:** State the expected duration of the project, including all follow-up and data analysis activities.

The expected duration of the project including all follow-up and data analysis is 48 months from trial initiation.

3. **Research Type/Phase: (Check all that apply)**

a. **Study Type**

Single Center Study

Multi-Center Study

Does the Yale PI serve as the PI of the multi-site study? Yes  No

Coordinating Center/Data Management

Other:

b. **Study Phase**  N/A

Pilot

Phase I

Phase II

Phase III

Phase IV

Other (Specify)

4. **Area of Research: (Check all that apply)** Note that these are overlapping definitions and more than one category may apply to your research protocol. Definitions for the following can be found in the instructions section 4c:

- |   |  |
|---|--|
|  Clinical Research: Patient-Oriented     |  Clinical Research: Outcomes and Health Services |
|  Clinical Research: Epidemiologic and Behavioral    |  Interdisciplinary Research                      |
|  Translational Research #1 (“Bench-to-Bedside”)     |  Community-Based Research                        |
|  Translational Research #2 (“Bedside-to-Community”) |  |

5. Is this study a clinical trial? Yes  No

*NOTE the current ICMJE (International Committee of Medical Journal Editors) definition of a clinical trial: “any research study that prospectively assigns human participants or groups of humans to one or more health-related interventions to evaluate the effects on health outcomes.” Health-related interventions include any intervention used to modify a biomedical or health-related outcome (for example, drugs, surgical procedures, devices, behavioral treatments, dietary interventions, and process-of-care changes). Health outcomes include any biomedical or health-related measures obtained in patients or participants, including pharmacokinetic measures and adverse events”*

If yes, where is it registered?

Clinical Trials.gov registry

Other (Specify)

Registration of clinical trials **at their initiation** is required by the FDA, NIH and by the ICMJE.

*If this study is registered on [clinicaltrials.gov](http://clinicaltrials.gov), there is new language in the consent form and compound authorization that should be used.*

For more information on registering clinical trials, including whether your trial must be registered, see the YCCI webpage, <http://ycci.yale.edu/researchers/ors/registerstudy.aspx> or contact YCCI at [contact])

6. Does the Clinical Trials Agreement (CTA) require compliance with ICH GCP (E6)?  
Yes  No

7. Will this study have a billable service? *A billable service is defined as any service rendered to a study subject that, if he/she was not on a study, would normally generate a bill from either Yale-New Haven Hospital or Yale Medical Group to the patient or the patient’s insurer. The service may or may not be performed by the research staff on your study, but may be provided by professionals within either Yale-New Haven Hospital or Yale Medical Group (examples include x-rays, MRIs, CT scans, specimens sent to central labs, or specimens sent to pathology). Notes: 1. There is no distinction made whether the service is paid for by the subject or their insurance (Standard of Care) or by the study’s funding mechanism (Research Sponsored). 2. This generally includes new services or orders placed in EPIC for research subjects.*

Yes  No

If answered, “yes”, this study will need to be set up in OnCore, Yale’s clinical research management system, for Epic to appropriately route research related charges. Please contact [[contact]](mailto:[contact])

8.. Are there any procedures involved in this protocol that will be performed at YNHH or one of its affiliated entities? Yes   x   No    *If Yes, please answer questions a through c and note instructions below. If No, proceed to Section III.*

a. Does your YNHH privilege delineation currently include the **specific procedure** that you will perform? **Yes**

b. Will you be using any new equipment or equipment that you have not used in the past for this procedure? **No**

c. Will a novel approach using existing equipment be applied? **No**

If you answered “no” to question 8a, or "yes" to question 8b or c, please contact the YNHH Department of Physician Services ([name]) for prior approval before commencing with your research protocol.

*Please note that if this protocol includes Yale-New Haven Hospital patients, including patients at the HRU, the Principal Investigator and any co-investigators who are physicians or mid-level practitioners (includes PAs, APRNs, psychologists and speech pathologists) who may have direct patient contact with patients on YNHH premises must have medical staff appointment and appropriate clinical privileges at YNHH. If you are uncertain whether the study personnel meet the criteria, please telephone the Physician Services Department at [contact]. **By signing this protocol as a PI, you attest that you and any co-investigator who may have patient contact has a medical staff appointment and appropriate clinical privileges at YNHH.***

**SECTION III: FUNDING, RESEARCH TEAM AND TRAINING**

1. **Funding Source:** Indicate all of the funding source(s) for this study. Check all boxes that apply. Provide information regarding the external funding source. This information should include identification of the agency/sponsor, the funding mechanism (grant or contract), and whether the award is pending or has been awarded. Provide the M/C# and Agency name (if grant-funded). If the funding source associated with a protocol is “pending” at the time of the protocol submission to the HIC (as is the case for most NIH submissions), the PI should note “Pending” in the appropriate section of the protocol application, provide the M/C# and Agency name (if grant-funded) and further note that University (departmental) funds support the research (until such time that an award is made).

PI	Title of Grant	Name of Funding Source	Funding	Funding Mechanism
----	----------------	------------------------	---------	-------------------

[name].	Toradol to Reduce Ureteroscopic Symptoms Trial (TRUST)	Yale Department of Urology	 Federal  State  Non Profit  Industry  Other For Profit  Other	 Grant-M#  Contract#  Contract Pending  Investigator/Department Initiated  Sponsor Initiated  Other, Specify:
			 Federal  State  Non Profit  Industry  Other For Profit  Other	 Grant-M#  Contract#  Contract Pending  Investigator/Department Initiated  Sponsor Initiated  Other, Specify:
			 Federal  State  Non Profit  Industry  Other For Profit  Other	 Grant-M#  Contract#  Contract Pending  Investigator/Department Initiated  Sponsor Initiated  Other, Specify:

IRB Review fees are charged for projects funded by Industry or Other For-Profit Sponsors. Provide the Name and Address of the Sponsor Representative to whom the invoice should be sent. *Note: the PI's home department will be billed if this information is not provided.*

**SECTION V: RESEARCH PLAN**

1. **Statement of Purpose:** State the scientific aim(s) of the study, or the hypotheses to be tested.

*The objective of this study is to evaluate the effect of a single intraoperative ketorolac injection on intra-operative narcotic use, postoperative pain and narcotic use, and hospital readmission rates in patients who undergo retrograde ureteroscopy for kidney and/or ureteral stone management.*

2. **Background:** Describe the background information that led to the plan for this project. Provide references to support the expectation of obtaining useful scientific data.

*The incidence and prevalence of urolithiasis in the United States has risen considerably over the past few decades.(1) Treatment for ureteral stones can include expectant therapy for asymptomatic and small stones,, shock wave lithotripsy (SWL) or ureteroscopy (URS) with lithotripsy for obstructing or symptomatic stones up to 15-20mm, and percutaneous nephrolithotomy for larger more complex stones.*

*Historically, SWL offered a non-invasive and effective intervention for the treatment of most symptomatic stones and was the preferred therapy. However, with advancement in ureteroscopic digital optics, miniaturization of scope caliber, improved flexibility and durability, and recognized better stone free rates, utilization of URS has steadily grown and is overtaking SWL as the preferred treatment modality for kidney stones. URS is accepted as the treatment of choice for lower ureteral stones and is associated with stone free rates of up to 100% by post-operative day 2.(2)*

*One limitation of URS is that post-operative pain due to intra-operative instrumentation and the common utilization of temporary ureteral stents can be challenging to manage. The complication rate for URS requiring postoperative hospital admission has been reported at up to 14%, with pain being the predominant complication.(4) This temporary post-operative pain and stent related colic is perhaps the greatest barrier, aside from surgeon skill, to the wider utilization of this URS over SWL, which has less efficacy but can be better tolerated. In addition to improving URS as a technology, we as physicians must improve the tolerance of URS for the patients.*

*Ketorolac is a non-steroidal anti-inflammatory drug (NSAID) available in oral or parenteral formulations. It is a highly effective analgesic with comparable potency to narcotics, non-*

*habit forming, and without the gastro-intestinal (e.g. nausea, ileus, constipation) or neurologic side effects seen with narcotics. Ketorolac use is generally safe for short durations limited to less than 5 days. Contraindications including NSAID allergy, renal insufficiency, NSAID induced asthma, peptic ulcer disease, bleeding diathesis, pregnancy/breast feeding, or advanced age. The peri-operative use of ketorolac had been limited due to bleeding concerns. However, surgical studies have shown that its use in appropriately selected patients does not result in increased clinically significant bleeding but does improve pain control over placebo with reduced narcotic use. (6)*

*It has been previously shown that in-patients who undergo ureteral stent placement following SWL, the use of ketorolac as an intravesical agent significantly decreased discomfort 1 hour after treatment in comparison to patients who did not receive the treatment.(5) The safety of this was also confirmed as there were no postoperative side effects from the instillation.(5)*

*Currently, there is currently no consensus on standard of care regarding intraoperative analgesia for ureteroscopy. A ureteral stent is utilized in about 90% of patient. Patients are discharged with a prescription for oral narcotics and stents are usually removed on post-operative day 5-7.*

*To the best of our knowledge there have not been any prospective studies that have evaluated the use of intraoperative ketorolac in patients who undergo URS, regardless of stent placement, to minimize postoperative pain. We hypothesize that patients who receive intraoperative ketorolac during URS will have improved outcomes with regards to postoperative pain assessment as well as decreased pain related hospital admissions in comparison to patients with no treatment.*

- 3. Research Plan:** Summarize the study design and research procedures using non-technical language that can be readily understood by someone outside the discipline. **Be sure to distinguish between standard of care vs. research procedures when applicable, and include any flowcharts of visits specifying their individual times and lengths.** Describe the setting in which the research will take place.

*This is an investigator-initiated, single-center, prospective randomized clinical trial evaluating the efficacy of intraoperative Ketorolac on post-operative pain in patients undergoing ureteroscopy at Yale-New Haven Hospital.*

*The study population will include anyone between the age of 18-80 who is undergoing elective ureteroscopy for management of stone disease without contraindication to ketorolac.*

*Patients who are being consented to undergo a ureteroscopy with [name] will be asked to participate in this study. There is currently no consensus on standard of care regarding intraoperative analgesia for ureteroscopy. There is wide variability in practice, some clinicians choose to administer intraoperative analgesia while others rely only on the sedation effects of general anesthesia. This study is being carried out to see if administration of Ketorolac during ureteroscopy provides a post-operative benefit in pain scores when compared to no treatment.*

The intervention group in this study will receive a one time dose of Ketorolac 30mg intravenously after undergoing general anesthesia. Because they will be under general anesthesia, they will not know if they received the medication. Following the procedure, the intervention group may continue to use Ketorolac as needed to manage pain. The only difference between the intervention group and the non-intervention group is the one time dose of intraoperative ketorolac.

The FDA approves Ketorolac as a nonsteroidal anti-inflammatory drug (NSAID), indicated for the short-term (up to 5 days in adults) management of moderately severe acute pain that requires analgesia at the opioid level.

Following assessment of eligibility and documentation of consent to participate in the study, patients will be randomized to receive intraoperative Ketorolac Tromethamine (Toradol®) **or not**. In the no-treatment group, participants will not receive a dose of intra-operative Ketorolac. Pain will be managed in the standard way with post-operative Ketorolac as needed. In the treatment group, participants will receive one dose of Ketorolac IV 30mg during the procedure. Randomization will occur by the attending anesthesiologist.

For this trial the investigators, surgical team, and patients will be blinded to the administration of the agent, which is given as an IV Push of 30mg. For patients who are older than 65 years or weight less than 50kg the dose will be adjusted to 15mg to minimize the risk of bleeding. The anesthesiologist will not be blinded as he/she will deliver the agent and because the use of ketorolac may alter their usage of other intra-operative agents and post-operative agents. The surgical team will be un-blinded post-operatively.

Following the procedure, patients will rate their pain using a visual pain assessment scale at 1 hour postoperatively and at the time of discharge from the recovery room. Once the patient is at home, they will fill out a validated survey that has questions related to pain. This will be filled out once a day for a total of 7 days following the procedure. In addition, we will provide a medication utilization diary sheet for the patient to record daily use of prescribed narcotic and other as needed over the counter medications such as acetaminophen and ibuprofen. This will also be done daily for a total of 7 days. The patient will be surveyed at their one-week postoperative visit using the same assessment. All adverse drug reactions will be recorded from time of administration to initial follow-up. The following is the study schedule:

Study Schedule	Preop	Intraop	1hr post op	2 hr post op	1 week
Assessments					
Consent	x				
History and Physical	x				
Urine Culture					
Post URS medication record			x	x	
Pain Questionnaire	x		x	x	x
Adverse Events		x	x	x	x

4. Genetic Testing N/A

A. Describe

- i. the types of future research to be conducted using the materials, specifying if immortalization of cell lines, whole exome or genome sequencing, genome wide association studies, or animal studies are planned
- ii. the plan for the collection of material or the conditions under which material will be received
- iii. the types of information about the donor/individual contributors that will be entered into a database
- iv. the methods to uphold confidentiality

B. What are the conditions or procedures for sharing of materials and/or distributing for future research projects?

C. Is widespread sharing of materials planned?

D. When and under what conditions will materials be stripped of all identifiers?

E. Can donor-subjects withdraw their materials at any time, and/or withdraw the identifiers that connect them to their materials?

- i. How will requests to withdraw materials be handled (e.g., material no longer identified: that is, anonymized) or material destroyed)?

F. Describe the provisions for protection of participant privacy

G. Describe the methods for the security of storage and sharing of materials

5. **Subject Population:** Provide a detailed description of the types of human subjects who will be recruited into this study.

*Only patients with the following indications for URS will be included: All patients who are undergoing elective ureteroscopy for management of stone disease without contraindication to ketorolac.*

6. **Subject classification:** Check off all classifications of subjects that will be specifically recruited for enrollment in the research project. Will subjects who may require additional safeguards or other considerations be enrolled in the study? If so, identify the population of subjects requiring special safeguards and provide a justification for their involvement.

- |  |  |  |
|--|--|--|
|  Children              |  Healthy                |  Fetal material, placenta, or dead fetus |
|  Non-English Speaking  |  Prisoners                         |  Economically disadvantaged persons      |
|  Decisionally Impaired |  Employees                         |  Pregnant women and/or fetuses           |
|  Yale Students         |  Females of childbearing potential |  |

NOTE: Is this research proposal designed to enroll children who are wards of the state as potential subjects?  Yes  No (If yes, see Instructions section VII #4 for further requirements)

7. **Inclusion/Exclusion Criteria:** What are the criteria used to determine subject inclusion or exclusion?

*Inclusion criteria*

*Kidney Stones requiring surgery  
Ureteral stones requiring surgery  
Able to undergo general anesthetic  
Willing and able to consent to treatment  
Willing and able to complete all questionnaires  
18 years of age and older*

*Exclusion criteria*

*Solitary Kidney  
Anatomic Bladder or ureteral abnormality  
Previous urinary diversion  
Interstitial cystitis  
Pregnancy  
Ectopic kidney  
Renal failure  
Coagulopathy  
Neurogenic bladder  
Transplanted kidney  
Indwelling foley catheter or suprapubic tube  
Chronic narcotic use  
Known contraindications to agent (NSAID allergy, renal insufficiency, NSAID induced asthma, peptic ulcer disease, bleeding diathesis, pregnancy/breast feeding, or advanced age)*

8. How will **eligibility** be determined, and by whom?

*Eligibility will be determined based on URS indications and inclusion and exclusion criteria. All patients will be determined eligible by [name]*

9. **Risks:** Describe the reasonably foreseeable risks, including risks to subject privacy, discomforts, or inconveniences associated with subjects participating in the research.

*Additional risks from participating in this trial include those associated with the use of ketorolac. This includes but is not limited to bruising at place of injection, indigestion, allergic reactions including anaphylactic shock, abdominal pain, abnormal bleeding, vomiting, diarrhea, constipation, gas, bloating, dizziness, drowsiness, sweating, nausea, ringing in the ears, & headaches.*

The delivery of pain medications during ureteroscopy require the use of an intravenous (IV) line. This is a safe procedure used in every surgery requiring general anesthesia. There is a slight chance that multiple needle-sticks will be needed to make sure the IV is placed correctly. The subject might feel a small amount of pain when the IV is placed but it does not last very long. A bruise or a minor infection might develop where the IV is placed. A bruise will go away by itself and it might help if you wrap a warm towel around your arm. Infections can also be treated if necessary.

**10. Minimizing Risks:** Describe the manner in which the above-mentioned risks will be minimized.

*The above mentioned risks will be minimized as a thorough medication history for each patient will be assessed. Those who are previously known to have adverse events with NSAIDS or specifically ketorolac will be excluded. In addition, medication dosing will be in compliance with federal drug administration recommendation. For severe allergic reactions such as anaphylaxis, all patients will be under monitored anesthesia care during the procedure and immediately postoperatively and as such under the care of individuals trained to recognize and treat this. Patients who are older than 65 may be more sensitive to the effects of ketorolac and clear the drug more slowly, so for this population we will dose reduce to 15mg. In addition, abdominal pain, nausea, vomiting, hyperventilation, peptic ulcers and/or erosive gastritis and renal dysfunction which have been associated with single dose ketorolac have resolved with medication discontinuation and for the purposes of this study, participants will only receive one dose and subsequently be discontinued on it.*

A bruise from the IV will go away by itself and it might help to wrap a warm towel around the arm. Infections can also be treated with antibiotics if necessary.

**11. Data and Safety Monitoring Plan:** Include an appropriate Data and Safety Monitoring Plan (DSMP) based on the investigator's risk assessment stated below. (Note: the HIC will make the final determination of the risk to subjects.) For more information, see the Instructions, page 24.

- a. What is the investigator's assessment of the overall risk level for subjects participating in this study? Greater than Minimal risk
- b. If children are involved, what is the investigator's assessment of the overall risk level for the children participating in this study? n/a
- c. Include an appropriate Data and Safety Monitoring Plan. Examples of DSMPs are available here <http://your.yale.edu/policies-procedures/forms/420-fr-01-data-and-safety-monitoring-plans-templates> for
  - i. Minimal risk
  - ii. **Greater than minimal**

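### The protocol contradicts itself on whether ketorolac may be used after surgery, and no described instrument names it, so any use after discharge would go unrecorded

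*Combined protocol and SAP*

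**What the plan says.** All of these places are in Section V of the combined protocol and SAP.

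- **Home diary (item 3, Research Plan).** Patients are given a sheet on which to "record daily use of prescribed narcotic and other as needed over the counter medications such as acetaminophen and ibuprofen". On duration: "This will also be done daily for a total of 7 days". The form itself is not reproduced.
- **Other medication record (item 3, study schedule).** A row called "Post URS medication record" is marked at the 1-hour and 2-hour columns and is blank at one week. The drugs it covers are not listed.
- **Further ketorolac, intervention arm (item 3).** "Following the procedure, the intervention group may continue to use Ketorolac as needed to manage pain".
- **Further ketorolac, no-treatment arm (item 3).** "Pain will be managed in the standard way with post-operative Ketorolac as needed".
- **Further ketorolac, risk section (item 10, Minimizing Risks).** "participants will only receive one dose and subsequently be discontinued on it".
- **Discharge prescription (item 2, Background).** "Patients are discharged with a prescription for oral narcotics". No ketorolac prescription is mentioned.
- **Blinding (item 3).** The anesthesiologist knows the allocation, and the plan accepts that this may change the choice of other drugs during and after surgery. The surgical team learns the allocation after the operation.
- **Analysis (item 12, Statistical Considerations).** The only medication data listed are baseline medications. No summary of post-operative ketorolac is planned.

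**The concern.** The arms are meant to differ by a single intra-operative dose of ketorolac. If the same drug may be taken again afterwards, in either arm and as needed, then later exposure is part of what each arm received, and a reader will want to know how much there was.

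The objectives in item 1 include postoperative pain and narcotic use. Ketorolac bears on both: item 2 presents it as a potent analgesic that reduces narcotic use. If it is used after surgery and not recorded, lower narcotic use in one arm could come from the intra-operative dose or from later ketorolac taken in place of a narcotic. A null pain result could mean that the dose does nothing at home, or that controls caught up by taking the drug later. The trial could not say which, nor report how far the control arm received the study drug at home.

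**Working it through.** The plan has no figure of its own on this point. The 63 per arm in item 12 contains no term for post-operative ketorolac, so there is nothing to reproduce. The check is a comparison of the text.

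1. **Is further ketorolac allowed?** Item 3 says yes for both arms, with no place or end stated. Item 10 says that there is one dose and then no more. Both cannot hold as written.

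2. **Would the diary catch it?** The description has two classes: the prescribed narcotic and over-the-counter drugs. Item 2 contrasts ketorolac with narcotics and classes it as an NSAID. The over-the-counter examples are acetaminophen and ibuprofen. Ketorolac is not named and belongs to neither class as described.

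3. **Would anything else catch it?** The schedule's medication record sits at 1 and 2 hours. It may capture doses given in the recovery room, but its contents are not listed. It is not marked at one week. The one-week visit is described as repeating the survey and collecting adverse events. The diary is thus the only described record of medication taken at home.

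4. **Could use differ by arm?** Yes, in two ways. As-needed use responds to pain, so an effective intra-operative dose would itself change the demand for later ketorolac. In addition, the anesthesiologist is unblinded throughout and the surgical team after the operation, so the supply could differ too.

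5. **What would that do to a home comparison?** Let p_C and p_T be the proportions of control and treated patients who use ketorolac at home, and let e be the mean fall in pain score among users. Assume that e is the same in both arms and simply adds to the effect of the intra-operative dose. Then:

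   observed difference = effect of the intra-operative dose without later use − (p_C − p_T) × e

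   - More use among controls (p_C > p_T) shrinks the difference.
   - More use in the treated arm (p_T > p_C) enlarges it.
   - Equal use leaves it unchanged.

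   Each proportion lies between 0 and 1, so the shift lies between −e and +e. The same form applies to narcotic use. The documents give none of p_C, p_T or e, so no narrower range can be derived, and the plan as described would not collect the home-use data needed to estimate p_C and p_T.

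**The case against.** The strongest reply is that home use is not part of this trial. Item 3 speaks only of use after the procedure, which may mean the recovery room. Item 2 names only oral narcotics at discharge, item 10 says that ketorolac stops after one dose, and Section X, item 3 describes it as a peri-operative drug whose cost is bundled with the procedure. A diary of the discharge narcotic plus over-the-counter drugs fits that regimen. Recovery-room doses may be caught by the early medication record, and the diary sheet may have a line for other medicines.

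Much of this stands. A reader might infer that patients do take ketorolac at home and that it is never counted. The documents do not establish either: home use is left open by silence, and neither form is shown. A reader might also take the labelled indication of up to 5 days, cited in item 3, as a study regimen covering most of the diary period. It describes the drug's approval and is not a schedule for this trial.

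The reply does not remove the contradiction between items 3 and 10. Nor does it identify any described instrument that names ketorolac. If further use is meant to be barred, a recorded entry is still how a deviation would be seen.

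A second reply is that as-needed use arises after randomisation, so the arms can be compared as assigned, with later analgesia as part of each strategy. That is correct and limits the point to interpretation.

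**Conclusion.** The point holds in conditional form. The protocol conflicts on whether ketorolac may be given again after the intra-operative dose. As described, no instrument names the drug, and none besides the diary covers medication at home. Any use after discharge would go unrecorded. Use before discharge may or may not be recorded.

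It would be tempting to conclude that the home pain and narcotic results could not be interpreted at all. The documents do not support that. The comparison as randomised remains valid; what is lost is the ability to separate the effect of the intra-operative dose from that of differing ketorolac use afterwards.

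No size can be put on this from the documents. It is nil if later use is absent or equal between arms, and otherwise depends on the gap in use and the effect per user. The conclusion assumes that the diary and the early record contain no more than their descriptions say. The change is worth making because it is cheap and because use that is not recorded at the time cannot be reliably recovered later.

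**What to change.** 1. Reconcile Section V, items 3 and 10, so that the protocol states once, for both arms, whether further ketorolac is allowed and, if so, where and until when. Which rule to adopt is for the investigators.
2. Add a ketorolac entry (dose, route, time) to the recovery-room medication record and to the 7-day diary, and list in the protocol which drugs each form covers. The entry measures exposure if further use is allowed and detects deviations if it is not.
3. In item 12, add a descriptive report of the number of ketorolac users and total dose by arm, placed beside the pain and narcotic results. Keep the comparison of arms as randomised as the main analysis.

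The cost is one line on each of two forms already planned, one descriptive table and a text correction. The sample size and visits do not change.
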